This study will be conducted according to the principles of the Helsinki Declaration. This protocol will be submitted to the Regional Committee for Health Research and Ethics, the Danish Data Protection Agency, and the Danish Medicines Agency for approval. Cooperation with the regional GCP unit will be initiated before the study is launched to ensure good clinical practice before during and after the study. The head of department for the experiment site has given the approval. The protocol will be registered at clinicaltrials.gov. All participants in this study have to give their oral and written consent before they can be included in the study. It is the investigators duty to inform the participant orally and in writing, so they are thoroughly informed about all aspects concerning participation in the study. The participant can at any point withdraw the consent concerning participation in the study. If a participant decides to do so it will not impair the relationship to the investigator or the doctors involved.

The clinical investigation shall not begin until the required approvals from the Local Ethics Committee, the Danish Data Protection Agency, and the Danish Medicines Agency have been obtained. Any additional requirements imposed by the Local Ethics Committee or regulatory authority will be followed.

15. Compensation to patients

The Department of Surgery, where participants are admitted, assumes the legal responsibility on behalf of the investigators and the investigators' assistants for all participants in the trial concerning any injury that is caused by the study procedures either directly or indirectly, assuming that the investigators and assistants have followed the guidelines given in this protocol and in any eventual additions to this protocol. In addition, it is also assumed that the study is performed scientifically and in coherence with existing rules and accepted techniques. The participants are in the case of injury or death without connection to the completion of the trial insured by the hospitals insurance. The participants will be informed that they are

covered by the public participant insurance, and if the participant wishes to complain, the participant will be informed on how to obtain help for this matter.

References

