The T-cells ability to infiltrate and be effective in the tumor microenvironment is regulated and effected by numerous cells and cytokines⁵. Thus, the research into modulating the tumor microenvironment has started so more patients can be treated with effective immunotherapies. A recent discovery has been the usage of intratumoral interventions as a way to directly affect the tumor and possibly sparing the patients of side effects of systemic treatment^{6,7}. An approach have been to use off-the-shelf vaccinations and administer them intratumorally where rotavirus and influenza virus vaccinations have been the most prominent^{6,7}. The effects of either vaccine was shown to be substantial when administered intratumorally but not intramuscularly. In vivo models of mice with injected tumors in both flanks where only one flank was treated also showed a systemic response in the form of regression of both the treated and non-treated flank⁷.

Both author groups focused on TILs in subsequent analyses of the tumors and both found that T-cell infiltration rose but interestingly also found that tumor cells upregulated PD-1 and CTLA-4 expression. A combination of rotavirus vaccination and anti-CTLA-4 therapy was conducted and showed a more prominent response, thus proving that a combination of the treatments complement each other⁷. Studies investigating the effects of systemic influenza vaccine in patients with colorectal cancer have shown an increase in unspecific NK cell activity⁸. The authors investigating intratumoral influenza vaccine also analyzed the tumors with Nanostring, a multiplex mRNA gene assay providing information on known

inflammatory and immune pathways, where they could show an increase in IFN-gamma, the key stimulator of NK cells⁶.

Aim of the study

The aim of this explorative phase II clinical trial is to establish the safety and efficacy of intratumoral influenza vaccine in patients with colorectal cancer, as an additive treatment prior to intended curative surgery.

Previous experience at Zealand University Hospital

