[name] [name] is the founder of Center for Surgical Science and Zealand Surgical Forum. He is one of the leading colorectal surgeons in Denmark. His primary investigational field covers optimization of colorectal cancer treatment and prognosis for the patients. Department of Surgery, Zealand University Department of endoscopy has all the necessary resources to perform this study. Only senior surgeons with high expertise in endoscopy will perform the procedures.

3. Methods

Objectives

Primary:

To investigate if intratumoral influenza vaccine is a safe treatment modality for tumor down staging prior to intended curative surgery in patients undergoing treatment for colorectal cancer.

Secondary:

To investigate if intratumoral influenza vaccine will induce immunologic invasion of the primary tumor

Tertiary:

To investigate if the treatment will induce a systemic immunologic response.

Quality of recovery

To assess quality of recovery for patients recruited into this trial. A quality of recovery questionnaire (QoR-15) will be given to patients pre- and post-treatment.

Study design

This is an explorative phase 2 clinical trial which will be conducted in two phases. The aim of this study is to establish the safety and efficacy of treating patients with early colorectal cancer with intratumoral influenza vaccine as a down staging and immune response enhancing treatment prior to intended curative surgery.

The first part of the study will be conducted as a pilot study. Six patients with histologically verified or clinically suspicious sigmoid colon cancer who are planned to undergo curative surgery will be included. Patients will be recruited from the Department of Surgery, Zealand University Hospital, Department of Surgery, Slagelse Sygehus and Department of Surgery, Sydvestjysk Sygehus after their case has been reviewed by the multidisciplinary team (MDT). Standard treatment involves intended curative surgery within two weeks after the diagnosis. The treatment will be performed within a few days and it will be ensured that the experimental treatment will not lead to a significant delay of intended curative surgery.

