- 1. Evaluation of serious adverse events
- 2. Evaluation of any adverse events reported.

Efficacy endpoints

The efficacy of the treatment will be evaluated according to the pathological examination of the surgical specimen. As such, final tumor staging, tumor regression grade (Mandard classification) T-cell subtype infiltration of the primary tumor and PD1/PDL-1 status before respective to after treatment are considered endpoints parameters. Furthermore, systemic immune responses will be evaluated through a multiplex gene assay, flow cytometry and NK cell activity analysis. A detailed evaluation of patient reported quality of recovery will be performed through repetitive administration of standardized questionnaires before the treatment with influenza vaccine (baseline), before surgery, postoperative day 2-3, and at follow-up (postoperative day 12-16).

4. Statistical considerations

Statistical considerations

The aim of this explorative study is to establish the safety and efficacy of treating patients with primary, rectal cancer and sigmoid colon cancer with intratumoral influenza vaccine prior to intended curative surgery.

Sample Size

This study will be the first to investigate intratumoral influenza vaccine in patients with colorectal cancer. Therefore, it is not possible to conduct formal sample size calculations. It was agreed at the coordinating investigator's pre sub-mission meeting that six patients were an appropriate initial sample size for the pilot study.

For the phase 2 study it was agreed that 24 patients were an appropriate initial sample size for this explorative study corresponding to 24 patients with either sigmoid colon cancer or rectal cancer.

Endpoints

Safety endpoint: Safety endpoints will be assessed continuously for serious adverse events as they
may arise. Review of the adverse event reports for events that may have occurred during the
investigation will serve as overall assessment of safety endpoints. Conclusions will be drawn
through full analysis of all reports rather than through statistical analysis.

2. Efficacy endpoint:

The Department of Pathology at Roskilde Hospital will objectively assess the surgical specimen after resection in accordance to standard guidelines (Mandard classification).

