The participants in this study are individuals over 18 years with histologically verified or clinically suspicious rectal cancer and sigmoid colon cancer, with no indication for neoadjuvant chemoradiotherapy prior to intended curative surgery. The study involves recruitment of 30 patients in total, 6 in the pilot phase of the study and 24 patients with either sigmoid colon cancer or rectal cancer in the second phase of the study.

Estimated time needed to recruit participants: 24 months

Patients will be recruited from Zealand University Hospital in the Region of Zealand, Denmark, Slagelse Sygehus in the region of Zealand, and Sydvestjysk Sygehus in the Region of Southern Denmark

Inclusion criteria

- Patients must be mentally capable of understanding the information given.
- Patients must give written informed consent.
- Clinically suspected or histologically verified malignant tumor of the rectum or sigmoid colon.
- Tumor described as passable at index endoscopy.
- Men or women aged at least 18 years.
- Case reviewed by MDT (surgery, radiology, oncology). Case considered curable with standard surgical resection.

Exclusion criteria

- Highly inflamed gastrointestinal tissue which is ulcerated and bleeding
- Ongoing immunosuppressive treatment.
- Concurrent treatment with an investigational medicinal product.
- Patients with any other clinical condition or prior therapy that, in the opinion of the investigator,
 would make the patient unsuitable for the study or unable to comply with the study recruitments.
- Advanced tumor stages, clinical UICC stage IV.
- Indication for neoadjuvant chemoradiation or chemotherapy prior to surgery
- Acute surgical resection.
- Pregnancy
- Any previous allergic reaction to influenza vaccine or constituents, egg and chicken proteins, neomycin, formaldehyde or octoxinol-9
- Acute febrile illness
- Acute infectious disease
- Influenza vaccine administered within 30 days before study inclusion

Discontinuation criteria

Trial subjects are withdrawn from the study if:

- The patient withdraws his or her consent
- The disease progresses so that the patient is in need of another treatment
- Investigator deems that withdrawal is in the best interest of the patient
- 6. Risks and side effects

Registration of adverse events

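### Safety is the primary objective, but its conclusion is to be drawn without statistical analysis and the sample sizes carry no precision, so it would have no stated uncertainty

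*Protocol*

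**What the plan says.** - **Aim and objective.** The Protocol's Aim of the study is "to establish the safety and efficacy of intratumoral influenza vaccine in patients with colorectal cancer", and section 4 repeats it: "The aim of this explorative study is to establish the safety and efficacy of treating patients". The primary objective in section 3 is worded more cautiously: "To investigate if intratumoral influenza vaccine is a safe treatment modality for tumor down staging".
- **Primary safety endpoints** (section 3, Study endpoints): evaluation of serious adverse events (SAEs) and of all reported adverse events (AEs). No acceptable or unacceptable rate is given for either.
- **How the safety conclusion is reached** (section 4, Endpoints): "through full analysis of all reports rather than through statistical analysis".
- **Sample size** (section 4, Sample Size): the study is the first in this setting. "Therefore, it is not possible to conduct formal sample size calculations". It was agreed that "six patients were an appropriate initial sample size for the pilot study" and that "24 patients were an appropriate initial sample size for this explorative study". Section 5 confirms the total: "The study involves recruitment of 30 patients in total, 6 in the pilot phase of the study".
- **Presentation of data** (section 4, Reporting of data and statistical analysis plan): number (%) is among the allowed summaries, while a 95% confidence interval is named only alongside the mean.
- **Safeguards.** Phase 2 opens only if the pilot has no SAE and breaks no stop rule (section 3, Study design). Events are reviewed as they arise and the study can be put on hold (section 3, Study endpoints). Section 6 lists stop rules.

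**The concern.** The primary question of the trial is whether the injection is safe. The Protocol fixes how that question is answered, and the method it fixes sets statistical analysis aside for the conclusion. An SAP that based the safety conclusion on an interval would contradict that sentence, so this is not a detail simply left for later.

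The two sample sizes come with no property attached. A reader is not told what event rate 6, 24 or 30 patients would probably reveal, or what rate a clean result would exclude. If few or no serious events occur, the final report could give a count, a percentage and a case-by-case judgement, with nothing to show how high the true rate might still be. A total of 30 patients leaves a good deal open, and the word establish invites a firmer reading than the data can bear.

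**Working it through.** **Inputs.** From the Protocol: 6 pilot patients, 24 phase 2 patients, and the pilot gate of zero SAEs. Assumed: 95% confidence (no level or sidedness is set for safety, so both forms are shown), all patients injected and evaluable, independent patients with a common risk.

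**1. The plan's own figure.** There is no calculation to reproduce. The total agrees: 6 + 24 = 30.

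**2. What zero events leaves open.** The exact binomial upper limit for 0 of n is 1 − 0.025^(1/n) for the two-sided 95% interval and 1 − 0.05^(1/n) for a one-sided 95% limit. It needs only n, not a prior rate.

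| Result | Two-sided 95% upper limit | One-sided 95% upper limit |
|---|---|---|
| 0/6 | 1 − 0.025^(1/6) = 45.9% | 39.3% |
| 0/24 | 1 − 0.025^(1/24) = 14.2% | 11.7% |
| 0/30 | 1 − 0.025^(1/30) = 11.6% | 9.5% |

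**3. A few events in 30.** From the beta quantiles, the Clopper-Pearson 95% intervals are 0.1% to 17.2% for 1/30, 0.8% to 22.1% for 2/30 and 2.1% to 26.5% for 3/30.

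**4. Chance of seeing at least one event in 30**, 1 − (1 − p)^30:
- p = 10%: 1 − 0.90^30 = 1 − 0.042 = 95.8%
- p = 5%: 1 − 0.95^30 = 1 − 0.215 = 78.5%

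**5. How much the pilot gate filters.** The chance of zero SAEs in 6 is (1 − p)^6: 73.5% at a true SAE rate of 5%, 53.1% at 10% and 26.2% at 20%. A passed pilot is therefore weak evidence about the rate.

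**6. Effect of the gate on the pooled figures.** For SAEs, all 30 are reached only after 0/6. The chance of a wholly clean trial is still (1 − p)^6 × (1 − p)^24 = (1 − p)^30, so the 0/30 limit and the detection chances in step 4 stand. Once an SAE has occurred, the pooled interval ignores that it had to fall among the later 24. This is a reason to show the 24 separately as well as pooled.

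**The case against.** The strongest reply is that this is an exploratory, single-arm, first-in-setting study in which a fixed number without a power calculation is common, and in which safety is rightly judged case by case. The Protocol has real safeguards: the pilot gate, continuous review, the possible hold and the stop rules. Interval methods and table layouts are also usual SAP content. Much of this stands. The number 30 is not in question, the case review is needed, and the absence of a named interval method would not on its own be a point. What remains is that the Protocol itself states how the primary conclusion is drawn, and that none of the safeguards states a rate that can be excluded.

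A reader might infer four stronger points that the document does not support:

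- *Statistics are barred from safety altogether.* The sentence concerns how conclusions are drawn. The general rule still allows numbers and percentages, and section 6 requires severity, seriousness and relationship to be recorded, with CTCAE classification.
- *The statement that no formal calculation is possible is false.* Deriving a size formally needs a rate to exclude, an interval width or a detection target, and none is given. The statement is defensible. What is lacking is the precision that the chosen size gives.
- *The trial fails because it cannot exclude 0.5%.* That figure in section 6 is the complication risk of the additional endoscopy, not a rate the trial set out to exclude. Excluding it with zero events would take 598 patients (one-sided 95%) or 736 (two-sided).
- *Few events will be declared proof of safety.* No success rule says so, and the primary objective says investigate. The risk lies in the unqualified aim together with a conclusion that has no interval.

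**Conclusion.** The point holds as a matter of missing uncertainty, not of a wrong sample size. The Protocol sets out to establish safety, draws that conclusion without statistical analysis, and attaches no precision to its sizes. A trial with no events would be compatible with a true rate of up to 11.6% over all 30 patients, 14.2% in the 24 alone and 45.9% in the pilot alone (exact two-sided 95% limits). The exploratory label excuses the lack of power, but not a primary conclusion with no stated uncertainty.

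These figures assume that all 30 patients are injected and evaluable; fewer would widen the limits. They cover only events from the day of treatment until surgery, because that is the recording window in section 6. The zero-event limits bear mainly on SAEs: section 6 lists several vaccine reactions as more frequent than 10%, so zero is an unlikely result for AEs of any kind. The trial can run as designed, but the wording should be changed before the results are reported.

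**What to change.** 1. **Section 4, Endpoints.** Keep the review of every report and replace the clause that sets statistical analysis aside. For example: *In addition to individual review, the number and proportion of injected patients with at least one SAE, and with at least one treatment-related AE by CTCAE grade, will be reported with exact (Clopper-Pearson) 95% confidence intervals for the pilot, the 24 phase 2 patients and all 30.*
2. **Section 4, Sample Size.** Keep the statement that no formal calculation was made and add: *With 30 treated patients, the chance of seeing at least one patient with an event is 96% if the true rate is 10% and 79% if it is 5%. If none is seen, rates above about 12% are excluded (exact two-sided 95% upper limit 11.6%; 14.2% for 0/24 and 45.9% for 0/6).*
3. **Aim of the study, section 3 (Study design) and section 4.** Replace establish, as applied to safety, with wording that limits the conclusion to this precision, such as describing safety and estimating event rates.

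The cost is a few sentences and one table. No extra patients or procedures are needed, and the necessary data are already to be recorded in the case report form. The downside for the sponsor is that the safety claim will read less favourably.

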tissue. Further, after the elective surgery, three samples of 0.5 cm³ will be collected from the tumor and adjacent normal tissue and stored for later analysis. Additionally, if pathological examination reveals positive lymph nodes (eg. lymph nodes with live cancer cells) three formalin fixated specimens of the lymph nodes will be stored in the biobank. In order to ensure uniformity, all tumor biopsy analyses will be performed when samples have been obtained from all participants. Any tumor tissue left from the analyses will be stored in "Dansk Cancer Biobank" for future research according to Danish law. The Biobank will be approved by the Danish Data Protection Agency. Tissue collected before the experimental treatment will be characterized and compared with tumor tissue obtained from the final surgical specimen. Additionally, histopathologic characterization will be performed according to current standards (pTNM staging and tumor regression grade). Specific immunohistochemical staining for PD-1/PD-L1 and conventional prognostic marker analysis will be performed on biopsies and the final surgical specimen. Tumor infiltration of T-cells and subtypes will be characterized according to the immunoscore classification system. Quality of Recovery (QOR15) will be evaluated at baseline, prior to surgery on admission to the Department of Surgery, post-operative day 2-3, and at follow-up day 12-16.

Study design:

	MDT conference
	Inclusion with clinical examination. Blood samples. EKG. Questionnaire
Day 0	Intratumoral influenza vaccine treatment
Day≥7	Surgery and preoperative blood samples and Questionnaire
POD 2-3	Blood samples and Questionnaire
POD 12-16	Blood samples and Questionnaire

Dosage

A single vial containing 0.5 ml of Influvactetra® influenza vaccine will be suspended in 2 ml of NaCl in one vial. The treatment will be administered in four quadrants where 0.5 ml will be deposited in each location.

Surgical procedure

Standard surgical procedure for rectal cancer and sigmoid colon cancer, respectively. Surgical treatment outlined by MDT.

Study endpoints

Safety endpoints

Safety evaluation will be performed via continuous assessment of safety parameters by reviewing events as they arise. We will conduct the pilot study in order to measure potential safety issues in a small cohort of patients before including patients in the phase 2 study.

The investigation will be put on hold if unacceptable safety issues are detected.

Primary safety endpoints:

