Furthermore, our aim is to investigate changes in immunological invasion in tumor tissue before and after intratumoral influenza vaccine. Finally, we intend to investigate the systemic response to intratumoral influenza vaccine.

Reporting of data and statistical analysis plan

After all participants have undergone treatment, the coordinating investigator will perform the statistical analyses. The analyses will begin with an exploration of the data to check for anomalies that might require data queries to be raised. Data will be presented as mean (95% confidence interval), median (interquartile range [IQR]), or number (%) as appropriate. The level of significance will be set at p<0.05. Data will be analyzed via parametric or non-parametric statistic depending on their distribution. Missing values, selection or exclusion of observations and variables and handling of missing values in the statistical analysis will be described carefully. Missing values will be filled in with last value available (Last Observation Carried

Forward – LOCF). A principal analysis will be performed according to the intention-to-treat principle (ITT). A per-protocol analysis will also be performed. For statistical analysis of data derived from the multiplex gene assay normalization and gene expression index calculation of probe intensities will be done, using the robust multi-array average (rma) method. Only perfect match probes will be used for data analysis. Regularized t-test will be used to calculate differences in gene expression between samples taken at different time sets. The Benjamini Hochberg method using the false discovery rate (FDR) will be used to correct for multiple hypothesis testing.

The results of this trial will be published in international or national peer-review journals regardless of negative, positive or inconclusive research results. In addition, the trial will be registered at www.clinicaltrials.gov and will be updated according to the study progress. In the event that part of the analysis is changed from the statistical analysis plan, these changes will be described and justified. Additional analyses that are not specified in the statistical analysis plan will be described at this stage and will be labeled as 'post-hoc' and the reason for their inclusion will be provided.

5. Participants

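### Blanket LOCF sets the treatment change to zero whenever a paired tissue marker or pre-surgery blood marker is missing, and fills missing postoperative QoR-15 scores from a different recovery state

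*Protocol*

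**What the plan says.** Protocol section 4, *Reporting of data and statistical analysis plan*, gives one rule for missing data: "Missing values will be filled in with last value available", named there as LOCF. No endpoint or visit is exempted. The principal analysis is by intention to treat, and the only other analysis named is this: "A per-protocol analysis will also be performed". The same paragraph promises a careful description of how missing values are handled. That is a reporting commitment and does not restrict the rule.

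The rule meets this measurement schedule:

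- **Tumour tissue, two time points** (section 3, *Study design*): "Tissue collected before the experimental treatment will be characterized and compared with tumor tissue obtained from the final surgical specimen". Under *Efficacy endpoints*, T-cell subtype infiltration and "PD1/PDL-1 status before respective to after treatment are considered endpoints parameters".
- **Blood, four time points** (section 7, *Blood samples*): before the vaccine, on admission for surgery, within 72 hours after surgery, and about 14 days after surgery.
- **QoR-15, four time points** (section 3): "Quality of Recovery (QOR15) will be evaluated at baseline, prior to surgery on admission to the Department of Surgery, post-operative day 2-3", and then at follow-up on day 12-16. Section 7 calls it a main outcome, scored 0 to 150 with higher being better.
- **Mandard regression grade and final stage**: assessed once, on the resected specimen.

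Section 5, *Discontinuation criteria*, withdraws a patient if "The disease progresses so that the patient is in need of another treatment".

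**The concern.** LOCF assumes that nothing changes between the last observed visit and the missing one. In this trial the vaccine lies between the first and second measurements, and the operation lies between the second and third. The carried value therefore predates the event whose effect is being estimated.

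The analyses at stake are the secondary objective (immune invasion of the tumour), the tertiary objective (systemic immune response) and QoR-15. There is a single treated group, so no control arm could offset the distortion. With 24 or 30 patients, a handful of filled values can move an estimate.

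**Working it through.** The protocol gives no expected missing rate, effect size or standard deviation, so there is no stated figure to reproduce. The rule is first traced through the schedule and then sized under labelled assumptions.

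**Step 1. What LOCF inserts**

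| Missing value | Value carried | Consequence |
|---|---|---|
| Tissue marker in the surgical specimen | Pre-treatment biopsy | Imputed change = 0 |
| Blood marker at the pre-surgery sample | Baseline | Imputed treatment change = 0 |
| QoR-15 at day 2-3, or at both postoperative visits | Pre-operative score | Any early fall is hidden |
| QoR-15 at day 12-16 only | Day 2-3 score | Recovery probably understated |
| Mandard grade, final stage | None exists | Rule cannot be applied |

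**Step 2. Size for a before/after marker**

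Inputs: n = 24 (phase 2) or 30 (both parts), from section 5. Assumptions: k values missing, unrelated to outcome; true mean change d = 0.6 SD; SD of change = 1. Let f = (n − k)/n.

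- Mean change under LOCF = f × d. Observed pairs keep d.
- Variance of change under LOCF = f(1 + d²) − (f d)².
- SE under LOCF = √(variance/n). SE from observed pairs = 1/√(n − k).

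Example, n = 24 and k = 5: f = 19/24 = 0.792. Variance = 0.792 × 1.36 − 0.475² = 0.851. SE = √(0.851/24) = 0.188, against 1/√19 = 0.229. The ratio is 0.82.

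| n | k | Mean kept (f) | SE ratio, LOCF to observed pairs | Mean/SE, LOCF | Mean/SE, observed pairs |
|---|---|---|---|---|---|
| 24 | 1 | 0.958 | 0.965 | 2.86 | 2.88 |
| 24 | 2 | 0.917 | 0.930 | 2.77 | 2.81 |
| 24 | 5 | 0.792 | 0.821 | 2.52 | 2.62 |
| 24 | 7 | 0.708 | 0.745 | 2.35 | 2.47 |
| 30 | 3 | 0.900 | 0.916 | 3.06 | 3.12 |
| 30 | 6 | 0.800 | 0.828 | 2.84 | 2.94 |
| 30 | 9 | 0.700 | 0.737 | 2.61 | 2.75 |

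The estimate is pulled toward zero and its interval is too narrow, because the inserted zeros count as data. The test statistic hardly moves.

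**Step 3. Size for QoR-15 at day 2-3**

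Overstatement of the mean = share missing × true fall. For an assumed fall of 20 to 40 points and 20% missing: 0.20 × 20 = 4 and 0.20 × 40 = 8 points.

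**Step 4. If missingness is informative**

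Assume the missing patients have a change of −2 SD and the others +0.3 SD, with n = 24.

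- 2 missing: truth = (22 × 0.3 − 2 × 2)/24 = 0.11; LOCF = 22 × 0.3/24 = 0.28; observed pairs = 0.30.
- 4 missing: truth = (20 × 0.3 − 4 × 2)/24 = −0.08; LOCF = 20 × 0.3/24 = 0.25; observed pairs = 0.30.

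Neither method recovers the truth here, and observed pairs are slightly further off than LOCF. This limits what the fix can claim.

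**The case against.** The case for leaving the rule alone has several sound parts.

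- **Scope.** A reader might infer that every efficacy endpoint is distorted. That is not so: Mandard grade and final stage are measured once, so LOCF cannot bias them. It is simply undefined for them.
- **QoR-15.** A reader might infer that every missing postoperative score is set to the pre-operative level. That holds for day 2-3, or when both postoperative scores are missing, but not when day 12-16 alone is missing.
- **Progression.** A reader might infer that LOCF hides progressing patients as unchanged. The documents do not support this as a general statement. Surgery normally follows within two weeks of diagnosis, stage IV disease is excluded, and cases must be curable by resection, so withdrawal for progression before surgery is likely to be rare. The protocol does not say that a withdrawn patient has no later sample. T-cell infiltration and PD-1/PD-L1 are also not measures of progression.
- **False positives.** Under random missingness the ratio of mean to standard error falls slightly rather than rises, so LOCF does not manufacture significance for an immune change.
- **Stakes.** The trial is explorative. Its primary safety endpoint is judged by review of reports without statistical analysis, and no decision rule in the protocol uses an imputed value.

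These points narrow the finding and lower its weight, but they do not rescue the rule. Attenuation is not harmless in a study meant to estimate an immune effect, and for QoR-15 it flatters early recovery. The per-protocol analysis is not described as a check on LOCF.

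**Conclusion.** The concern holds for three groups of results: the paired tissue markers, the blood markers missing at the pre-surgery sample, and QoR-15. It should be fixed before analysis, but it does not threaten the trial's primary conclusion on safety.

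For the paired markers, under missingness unrelated to outcome, the estimated mean change is (1 − m) of the truth, where m is the share missing: 90%, 80% and 70% at 10%, 20% and 30%. With 5 of 24 missing and a true change of 0.6 SD, the standard error is about 0.82 of the observed-pairs value. With only 1 of 24 missing the shrinkage is about 4%, so the practical size depends on a rate that the protocol does not state. The QoR-15 overstatement of 4 to 8 points at day 2-3 rests on an assumed fall of 20 to 40 points and 20% missing.

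The zero imputed change and the lack of anything to carry for grade and stage follow from the schedule and need no assumption.

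**What to change.** Delete LOCF from section 4 and replace it with the following:

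1. Analyse markers with one before-value and one after-value on observed pairs.
2. Analyse QoR-15 and the repeated blood markers with a likelihood-based mixed model on all observed values, with time as a factor and patient as a random effect, and without imputation.
3. Report the number of missing after-values for each endpoint, and the reason for each one.
4. List patients withdrawn for progression separately, as an outcome. This is needed because observed-pair analysis does not remove bias from informative withdrawal, as step 4 of the working shows.

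The cost is wording only, with no extra patients, visits or samples. The downsides are slightly fewer values in the paired tests, and reliance on missingness being unrelated to the unobserved value. The second should be stated openly in the report.
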